3.9 Pharmacokinetics

MEDI-551 concentration will be summarized descriptively by visits separated by AQP4-IgG seropositive and seronegative NMO/NMOSD subjects. Mean MEDI-551 concentration versus time data will be plotted by AQP4-IgG seropositive and seronegative subjects. PK parameters will be estimated using noncompartmental methods. PK parameters will be listed by AQP4-IgG seropositive and seronegative NMO/NMOSD subjects and summarized descriptively.

Population PK or PKPD analysis may be conducted to include the exploratory analysis to identify the covariate that affect MEDI-551 PK or to investigate the relationship between MEDI-551 PK, PD and response as appropriate.

4 MULTIPLICITY ADJUSTMENT

The study is designed to strongly control the overall 2-sided Type I error rate of $\alpha = 0.05$ based on the Bonferroni-based chain procedure ([Bretz et al, 2009](#); [Millen and Dmitrienko, 2011](#)). The primary null hypothesis will be hierarchically tested first at $\alpha = 0.05$ in the AQP4-IgG seropositive cohort, and, if significant, it will be further tested in the ITT population at $\alpha = 0.05$. If and only if the treatment group comparison is statistically significant within the ITT population, secondary hypotheses will be tested. Null hypotheses for the 4 key secondary endpoints will follow the same sequential testing strategy as the primary analysis (testing within seropositive subjects first, followed by the ITT population if the comparison

within seropositive subjects is statistically significant). Each secondary hypothesis will be initially tested based on the Bonferroni method at $\alpha = 0.05/4 = 0.0125$. If the null hypothesis for a particular secondary endpoint is rejected across both the seropositive and the ITT populations, the Type I error saved will be propagated equally to other non-rejected sets of secondary null hypotheses. The testing procedure will be repeated until all null hypotheses are rejected or no further null hypothesis can be rejected. Details are described in Appendix 3.

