4.4 Study Suspension or Termination

The Sponsor reserves the right to temporarily suspend or terminate enrollment, RCP, OLP or the entire study at any time for the following reasons:

- 1 The incidence or severity of AEs in this or other studies indicates a potential health hazard to subjects
- 2 Subject enrollment is unsatisfactory
- 3 Non-compliance that might significantly jeopardize the validity or integrity of the trial
- 4 Sponsor decision to terminate development
- 5 Sponsor decision to terminate the trial based on a planned futility analysis
- 6 Recommendation of the independent DMC to discontinue enrollment and transition subjects from the RCP to the OLP due to evidence of efficacy and safety
- 7 Any other reason which justify this action/actions.

If MedImmune determines that temporary suspension or termination of the study is required, MedImmune will discuss the reasons for taking such action with all participating investigators (or head of the medical institution, where applicable). When feasible, MedImmune will provide advance notice to all participating investigators (or head of the medical institution, where applicable) of the impending action. In the case of the Sponsor discontinuing enrollment upon recommendation of the independent DMC based on evidence of efficacy and safety, subjects in the RCP at the time enrollment is terminated will be given the option to enter the OLP. The rationale for such a decision will be shared and discussed with investigators, IRBs, ethic committees, and regulatory agencies where appropriate. In addition, detailed procedures for transition of patients from the RCP to the OLP will be provided to the investigators in such a case.

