The data cutoff date for the primary analysis will be when the last subject completes the discontinuation visit following the 67th AC-determined attack, after all subjects complete the RCP if 67 AC-determined attacks do not occur, or after all subjects complete the EDV following discontinuation of enrollment upon recommendation of the independent DMC based on evidence of efficacy and safety. Subjects who are in the RCP when a total of 67 AC-determined NMOSD attacks have occurred or when enrollment is discontinued upon recommendation of the DMC based on evidence of efficacy and safety will discontinue the RCP as outlined in Section 4.5.1.2.

Since some AC-determined attacks may not be assessed within the assessment windows, a broader window will be used for primary analysis. Only AC-determined attacks with an assessment visit scheduled within 120 hours (5 days) of reporting symptoms and all assessments done within 10 days of an Assessment Visit will be included in the primary analysis. AC-determined attacks not included in primary analysis will be included in other supportive analyses. Sensitivity analysis will be conducted to assess the impact of the loss of any AC-determined attacks outside of the identified assessment window.

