Figure 2.3-1	Study Flow Diagram.....	16
Figure 3.3.1-1	Subject Disposition.....	23
Figure 3.7.1-1	Visual definition of TEAEs during different study periods.....	45
Figure 7-1	Neuromyelitis Optica Spectrum of Disorders Relapses Before and After Treatment with Azathioprine for 70 Patients with More Than 12 Months Follow Up.....	61
Figure 7-2	Attack Frequency Before, During, and After Eculizumab Treatment.....	62
Figure 7-3	Relapses in Patients with Neuromyelitis Optica Before and After Treatment with Rituximab.....	62
Figure 7-4	Disease Course of Patients Treated with Rituximab.....	63
Figure 7-5	Relapses in Patients with Neuromyelitis Optica Before and After Treatment with Rituximab.....	64
Figure 7-6	Estimated Predictive Power Against Observed Interim Treatment Effect When 50% of AC-determined NMO/NMOSD Attacks are Available.....	66
Figure 7-7	Multiplicity Adjustment Strategy.....	68
Figure 7-8	Agreement between Investigator and AC determination of Attacks.....	75

LIST OF APPENDICES

Appendix 1	Sample Size Calculation.....	60
Appendix 2	Details of Futility Analysis.....	68
Appendix 3	Type I Error Control.....	69
Appendix 4	Neuromyelitis Optica Attack Severity Score.....	71
Appendix 5	WMWodds approach for mRS score analysis.....	75
Appendix 6	Kappa Statistic for Investigator and AC-determined Attack Agreement.....	77

Amendment History

Date	Description of Change
October 18, 2018	
 • Amendment History: Oct 19, 2016 should be Oct 31, 2016 • Sections 2.2.1, 2.2.1.1, 2.2.1.3, 2.2.1.4 and 3.4.1.3: Introduced language related to changes in the study resulting from the Sponsor’s decision to accept recommendations from the DMC, based on evidence of efficacy and safety, to stop study enrollment and allow subjects in the RCP at that time the option to enter the OLP • Section 3.1.3: Only major protocol deviation will be summarized by category. • Section 3.4.1.4: A sensitivity analysis of the primary efficacy endpoint was added to analyze the date up to and including January 27, 2017.

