3 STATISTICAL METHODS

3.1 General Considerations

All statistical calculations will be primarily performed using SAS. All data will be presented in the form of listings sorted by treatment and subject number. Tabular summaries will be presented primarily based on the following grouping:

- Stratification: ‘AQP4-IgG seropositive’, ‘AQP4-IgG seronegative’ and ‘All subjects’
 - Treatment: Placebo and MEDI-551 300 mg (nested within each level of stratification)

For pretreatment data (demographics, baseline characteristics, medical/disease history, etc.), an ‘overall’ group combining both treatment groups will also be added to the presentation.

Categorical data will be summarized by the frequency counts and percentage of subjects in each category. Percentages will be calculated based on non-missing observations where applicable. Continuous variables will be summarized by descriptive statistics including number of observations, mean, standard deviation (SD), median, minimum, and maximum. In general, unless stated otherwise, baseline will be defined as the last value prior to first dose of IP. Missing baseline evaluations will not be imputed and will be considered missing.

Unless otherwise stated, all efficacy analyses will be done with a two-sided test at 5% significance level. Where appropriate model based estimates will be presented with their two-sided 95% confidence interval (CI) and p-values. Categorical data analyses using the Pearson chi-square test will be substituted by the Fisher’s exact test if greater than 20% of expected contingency table cell counts are less than 5.

Table 3.1-1 provides an overview of analysis milestones for this study.

Table 3.1-1 Overview of Analysis Milestones

Type of Analysis	Analysis milestones	Data to be analyzed
Unmasked futility analysis	When approximately 34 AC-determined attacks occur are observed (See Section 5)	Cumulative data on attack
Primary analysis	All subjects complete the RCP	All the data (including OLP and SFP) available at the time of database snapshot
Annual update of efficacy and safety	On an annual basis after the primary analysis	Cumulative safety and efficacy data (all study periods)
Final analysis	All subjects complete the SFP (or withdraw)	Cumulative safety and efficacy data

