3.4.1.3 Primary Efficacy Analysis

The following are the null and alternative hypotheses associated with the primary endpoint:

$$H_{01}: HR^+ = 1 \text{ vs } H_{11}: HR^+ \neq 1,$$

$$H_{02}: HR^{ALL} = 1 \text{ vs } H_{12}: HR^{ALL} \neq 1,$$

where HR^+ indicates the hazard ratio of AC-determined NMO/NMOSD attack for MEDI-551 relative to placebo in AQP4-IgG seropositive subjects. HR^{ALL} denotes the same quantity for the ITT population. The treatment effect in the seropositive cohort will be defined as the relative reduction in HR^+ ; ie, $100 \times (1 - HR^+)$. A value of $HR^+ < 1$ or a positive value of relative reduction will indicate the efficacy of MEDI-551 compared to placebo in the seropositive cohort. Similar interpretations will hold for HR^{ALL} . For the current study, the target treatment effect of 60% implies a hazard ratio (HR) of 0.4.

For the AQP4-IgG seropositive cohort, the treatment effect will be assessed using the Cox proportional hazards model with treatment indicator (MEDI-551 or placebo) as an explanatory factor; whereas for the ITT population, the model will also include serostatus as an additional explanatory factor. The HR of MEDI-551 versus placebo will be estimated together with its associated 95% CI. The SAS PROC PHREG will be used for fitting this model. Subjects who complete the Day 197 visit of the RCP or discontinue the study before Day 197 for reasons other than an AC-determined NMO/NMOSD attack will be censored in this model at the time of the Day 197/discontinuation visit.

An indicator variable for Japan versus non-Japan region will not be included in the Cox regression model due to the low number of anticipated Japanese subjects. An evaluation of consistency of treatment effect in Japanese subjects with that observed in the global study will be determined.

The data cutoff date for the primary analysis will be when the last subject completes the discontinuation visit following the 67th AC-determined attack, or after all subjects complete the RCP if 67 AC-determined attacks do not occur, or when the last subject completes the discontinuation visit following discontinuation of enrollment upon recommendation of the DMC based on evidence of efficacy and safety. Subjects who are in the RCP when a total of 67 AC-determined NMOSD attacks have occurred, or when enrollment is discontinued upon

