5 INTERIM FUTILITY ANALYSIS

An unmasked interim analysis will be conducted for futility assessment by an independent Data Monitoring Committee when approximately 34 (50% of the total planned AC-determined) NMO/NMOSD attacks occur in this study. The assessment of futility will be based on predictive power, which is based on the average conditional power calculated using the observed treatment effect trend and associated variability at the time of interim analysis to predict the final study outcome. All available subjects at the time of interim data cut will be included in the futility analysis. Details are provided in Appendix 2.

To be consistent with the hypothesis testing of the primary efficacy analysis as described in Section 3.4.1.3, the primary efficacy endpoint, time (days) from Day 1 to onset of an AC-determined NMO/NMOSD attack on or before the end of RCP, will be analyzed in the AQP4-IgG seropositive cohort as well as the ITT population for the interim futility analysis. The events to be included in the futility analysis will follow the methods described in the Section 3.4.1.1.

For the AQP4-IgG seropositive cohort, the treatment effect will be assessed using a Cox proportional hazards model with treatment indicator (MEDI-551 or placebo) as an explanatory factor; whereas for the ITT population, the model will also include serostatus as an additional explanatory factor. Subjects who have completed the RCP without having an AC-determined NMO/NMOSD attack will be censored on the date of completing RCP (Day 197 visit date). Subjects who have discontinued from the RCP for reasons other than an AC-determined NMO/NMOSD attack will be censored on the day of discontinuation from RCP (discontinuation visit date). Subjects who are ongoing in the RCP will be censored on the date of interim data cut. The SAS PROC PHREG will be used to fit this Cox proportional hazards model.

The predictive power based on the empirical trend observed at the interim analysis will be calculated by

$$\Phi \left[\frac{Z(t) - \sqrt{t}Z_{\alpha/2}}{\sqrt{1-t}} \right],$$

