The alpha allocation rule is specified in Table 7-6. Specifically, the null hypothesis S1 receives the initial weight of 1 (ie, it is tested at the full $\alpha = 0.05$) and the other null hypotheses receive zero weights. The alpha propagation rule is specified in Table 7-7. The alpha propagation rules are defined using transition parameters, eg, the first row in Table 7-7 shows that the fraction of the Type I error rate used in testing the null hypothesis S1 will be transferred to the null hypothesis O1 if the null hypothesis S1 is rejected. Similarly, if the null hypothesis O1 is rejected, the available Type I error rate will be split equally among the null hypotheses S2, S3, S4, and S5 (a quarter of the available Type I error rate will be allocated to each null hypothesis). The alpha allocation and alpha propagation rule uniquely define the Bonferroni-based chain procedure and the associated multiplicity-adjusted p-values can be computed using Algorithm 2 given in [Bretz et al \(2009\)](#).

Table 7-6 Alpha Allocation Rule	
Hypothesis	Initial Alpha Allocation
S1	α
S2	0
S3	0
S4	0
S5	0
O1	0
O2	0
O3	0
O4	0
O5	0

Table 7-7 Alpha Propagation Rule										
Hypothesis	S1	S2	S3	S4	S5	O1	O2	O3	O4	O5
S1	0	0	0	0	0	1	0	0	0	0
S2	0	0	0	0	0	0	1	0	0	0
S3	0	0	0	0	0	0	0	1	0	0
S4	0	0	0	0	0	0	0	0	1	0
S5	0	0	0	0	0	0	0	0	0	1
O1	0	1/4	1/4	1/4	1/4	0	0	0	0	0
O2	0	0	1/3	1/3	1/3	0	0	0	0	0
O3	0	1/3	0	1/3	1/3	0	0	0	0	0
O4	0	1/3	1/3	0	1/3	0	0	0	0	0
O5	0	1/3	1/3	1/3	0	0	0	0	0	0

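### Strong Type I error control is claimed with the full 0.05 for the primary tests, but no efficacy rule is stated for the DMC stop that can set the primary cutoff

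*SAP*

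**What the plan says.** **The claim.** SAP section 4: "The study is designed to strongly control the overall 2-sided Type I error rate", at 0.05. SAP Appendix 3 puts all of the initial alpha on S1: "the null hypothesis S1 receives the initial weight of 1". If S1 is rejected, O1 is tested at 0.05; if O1 is rejected, 0.0125 goes to each of S2-S5. The protocol makes the same claim in the Synopsis, section 4.8.9 and Appendix 11.

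**The stop.** Protocol 4.4 lists among the reasons for suspending or ending parts of the study: "Recommendation of the independent DMC to discontinue enrollment and transition subjects from the RCP to the OLP due to evidence of efficacy and safety". Such a stop also sets the data cutoff for the primary analysis. In SAP 3.4.1.3 the cutoff can fall "when the last subject completes the discontinuation visit following discontinuation of enrollment upon recommendation of the DMC based on evidence of efficacy and safety". In Protocol 4.8.3.1 it can fall "after all subjects complete the EDV following discontinuation of enrollment upon recommendation of the independent DMC based on evidence of efficacy and safety".

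**The stop was used.** The SAP Amendment History entry of 18 October 2018 introduces text following the sponsor's "decision to accept recommendations from the DMC, based on evidence of efficacy and safety, to stop study enrollment". Protocol section 9, Amendment 6 (11 October 2018), records the same decision.

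**The looks.** Protocol 4.8.8 has the unmasked DMC review clinical outcome data at specified regular intervals and receive real-time reports of new attacks, with further detail left to a separate charter. The only interim given a decision rule is for futility: "An unmasked interim analysis will be conducted for futility assessment by an independent Data Monitoring Committee when approximately 34" attacks have occurred (SAP section 5; also Protocol 4.8.10).

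**The mitigation.** Sensitivity analysis 8 in SAP 3.4.1.4 counts attacks up to 27 January 2017 and censors the remaining subjects on that date. The SAP explains that a DMC recommendation to stop enrollment and conclude the randomized period came as early as that day.

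**The concern.** A chain of this kind divides alpha among different null hypotheses. It takes for granted that each is tested once, at a time that does not depend on the accumating comparison. If an unmasked committee can look at attacks by arm more than once and end the randomized period because the result is favourable, the time of the final test depends on the data. Testing at an unadjusted 0.05 then no longer guarantees a 0.05 error rate. A stated boundary with matching levels would restore the guarantee, but neither document gives an efficacy boundary, a count of looks, a spending function or an adjusted final level.

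The primary p-values and confidence intervals depend on this property. So do the eight key secondary hypotheses (S2-S5 and O2-O5), which can be tested only after S1 and O1 are rejected.

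**Working it through.** **1. The plan's own figures.** SAP Appendix 1 gives E = [(z(0.975) + z(0.90)) / ln HR]² × (r+1)²/r, with HR = 0.4 and r = 3. Then [(1.960 + 1.282) / (-0.916)]² × 16/3 = 66.75, which rounds up to the stated 67. Also 0.05/4 = 0.0125, as stated. Both use the whole 0.05, so nothing is reserved for an efficacy look.

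**2. What the chain covers.** The propagation table passes alpha from S1 to O1, from O1 to S2-S5, from each of these to its ITT counterpart, and then among the remaining secondary endpoints. No entry refers to time or to a repeat test of S1 or O1.

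**3. One look, no further information.** Treat a single primary hypothesis as a null Brownian path. Put one look at 34 of 67 attacks, where t = 34/67 = 0.507 and the correlation with the final statistic is √t = 0.712. The DMC stops if Z > c; otherwise the final test is at 67 attacks. Success means Z > 1.96 at whichever analysis is final. Benefit-direction error = 1 − Φ₂(c, 1.96; 0.712):

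- c = 1.96: 0.0414
- c = 2.576 (two-sided p<0.01): 0.0272
- c = 3.291 (two-sided p<0.001): 0.0251

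The nominal value is 0.0250. For c = 1.96, adding the roughly 2.5% in the harm direction gives about 6.6% two-sided, against 5%.

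**4. More looks, and information added after the DMC acts.** The documents fix neither, so both are assumptions. Four schedules were used: one look at 34/67; two at 35% and 65% of information; four at 30, 50, 70 and 90%; and seven equally spaced from 25% to 85%. After the DMC acts, a further 0 to 50% of information accrues (capped at 100% in total) before the final test at Z > 1.96. Benefit-direction error, as the range over the four schedules (nominal 2.5%):

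| DMC acts at | +0% | +5% | +15% | +30% | +50% |
|---|---|---|---|---|---|
| Z > 1.96 | 4.1-7.8% | 3.4-5.0% | 3.0-3.8% | 2.7-3.1% | 2.5-2.7% |
| p < 0.01 | 2.7-3.4% | 2.7-3.3% | 2.7-3.0% | 2.6-2.7% | 2.5-2.6% |
| p < 0.001 | 2.5-2.6% | 2.5-2.6% | 2.5-2.6% | 2.5-2.6% | 2.5-2.6% |

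These come from numerical integration, and simulation with 2 million paths per cell agreed. They are scenarios, not bounds.

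**5. Which column applies.** The documents do not settle it. Subjects are to leave the randomized period preferably within 14 days of the stop (SAP 3.4.1.3), which points to the left-hand columns. If the relevant recommendation was that of 27 January 2017, it preceded Amendment 6 (11 October 2018) by 622 days and the SAP change (18 October 2018) by 629, which points to the right.

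**6. Sensitivity analysis 8.** It shows how far the result depends on data after 27 January 2017. Its cut is a date on which the DMC made a recommendation, and it changes no significance level, so it cannot restore the error guarantee.

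**The case against.** The strongest reply is that the rule may exist elsewhere. Protocol 4.8.8 says the review intervals are specified and refers to a DMC charter, which is not among these documents. That stands: what is established is that the protocol and SAP do not secure the claim, not that no rule was ever set. But the SAP, which makes the claim and sets the levels, cites no such rule, and an unchanged 0.05 need not match whatever the charter contains.

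Second, the large figures need a committee that acts at nominal significance on the same statistic that is later tested, with almost nothing accruing afterwards. The recommendation is described as resting on efficacy and safety together, not on one Z value, and under a strict threshold the inflation is trivial. This also stands, and the case for a change does not rest on the 7.8%.

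Third, the futility look costs no Type I error. Correct, and it is not the complaint.

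A reader might also infer from sensitivity analysis 8 that the trial had crossed an efficacy threshold in January 2017 and was then run on. The documents do not support that. The SAP does not say what that recommendation was based on, and the SAP amendment of 27 February 2017 and Protocol Amendment 4 (8 March 2017) show the study continuing with a larger sample size.

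**Conclusion.** The concern holds as a gap between a stated property and the rules meant to deliver it. Strong control at two-sided 0.05 is not secured by the protocol and SAP when the primary cutoff is a DMC stop made partly on efficacy. This is more than missing detail, because applying the stated 0.05 rule does not by itself yield the stated property and the sponsor has accepted such a stop. It needs correcting before unmasking.

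The size is unknown. In the scenarios, the benefit-direction error runs from 2.5-2.6% to 7.8% (7.8/2.5, about three times nominal), depending on the DMC's threshold, the number and timing of looks, and the information added afterwards, all of which are assumed here. A reader might conclude that the error rate is inflated. The documents do not show that: a strict rule in the charter would make the excess negligible. Confidence is high for the omission and the unsupported claim; no particular inflation or boundary is asserted.

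**What to change.** Before unmasking, amend SAP 3.4.1.3, section 4 and Appendix 3, and the matching protocol text (Synopsis, 4.8.9 and Appendix 11):

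- (a) List every unmasked review that compared attacks by arm, with its date and the seropositive and ITT attack counts. Include the futility look and any review behind the 27 January 2017 recommendation.
- (b) State or cite the efficacy rule the DMC used. Set the levels for S1 and O1, and the level passed on to S2-S5, to match that rule and all looks taken.
- (c) If no prespecified rule exists, withdraw the strong-control claim for an efficacy-based cutoff and label the p-values nominal. Report, as a supportive analysis, whether S1 and O1 cross a conservative spending boundary that counts every look actually taken.

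The cost is wording in both documents, plus look dates and attack counts from the DMC statistician. It needs no patients and no new data. The downside is that the stated levels may become slightly less favourable.
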